3.8 Center pooling strategy

Geographic regions have been categorized as North America, Western Europe, Eastern Europe, and Asia. [Table 3-1](#) displays the geographic regions with corresponding countries.

Table 3-1: Region definitions

Region	Countries
North America	United States
Western Europe	Belgium, France, Germany, Netherlands, Spain, United Kingdom
Eastern Europe	Bulgaria, Czech Republic, Hungary, Poland
Asia	China, Japan, Turkey

If the percentage of randomized study participants is less than 10% in a region, then regions will be combined to create a new geographic region stratum for efficacy modeling, so that there are no modeling convergence issues across efficacy variables. This new pooled geographic region stratum will then be used for any modeling (including MI, logistic regression and mixed model) including subgroup analyses.

3.9 Coding dictionaries

Medical history and AEs will be coded using the Medical Dictionary for Regulatory Activities (MedDRA[®]) version 19.0. Medications will be coded using the World Health Organization Drug Dictionary (WHO-DD) version SEP2020 or later. Medical procedures will not be coded.

To maintain consistency across studies in the bimekizumab development program, the dictionary versions will be held constant to support consistency of coding in the regulatory submissions.

3.10 Changes to protocol-defined analyses

The following changes from the protocol will be considered:

- The protocol mentions that subgroup analysis using descriptive statistics will be performed on the primary efficacy variable. However OR for the comparison of bimekizumab versus placebo and associated 95 % CI will be calculated. See Section 8.1.3 for further details.
- Race will be analyzed as additional subgroup variable.
- The Maintenance Set has been added as additional analysis set.
- The primary/main analysis of continuous secondary efficacy endpoints which are part of the sequential testing procedure, as well as the components of the primary ASAS40 endpoint, will use a reference-based imputation method.

3.11 Changes related to COVID-19

The impact of the COVID-19 pandemic on study procedures/conduct and on the primary efficacy endpoint and safety endpoints (TEAEs, serious TEAEs, and study withdrawal due to TEAEs) will be investigated and additional analysis outputs will be provided as appropriate. These additional analyses were not planned as part of the protocol as the pandemic was not ongoing at the time of protocol finalization.

These additional analyses will include analyses by period of the COVID-19 pandemic (prior/during/post) as defined in Section 3.2.2.2.

These additional analyses are described in the following sections:

- Study participant disposition (Section 5.1)
- Details of impacted visits and effects on collection and reporting of efficacy data (Section 5.3)
- Protocol deviations (Section 5.3)
- Exposure (Section 10.1.4 and Section 10.1.5)
- Adverse events (Section 10.2)

In addition, the primary analysis for the primary efficacy endpoint will be repeated by timing of the Week 16 Visit relative to the start and end of the COVID-19 pandemic (see Section 8.1.4.8).

4 STATISTICAL/ANALYTICAL ISSUES

4.1 Adjustments for covariates

The primary efficacy analysis that will investigate the treatment effect will be adjusted for:

- Prior TNF α inhibitor exposure (yes, no), and
- Region (Asia, Eastern Europe, North America, Western Europe)

However, prior TNF α inhibitor exposure may be dropped from the model in order to achieve model convergence (ie, in case the likelihood maximization algorithm failed to converge). If convergence is still not obtained, then region may instead or also be dropped from the model. This will be decided at the time of the table creation and clarified in respective table footnotes. Finally, in the case of the continuous secondary endpoints of the testing hierarchy, if the

reference-based multiple imputation model still does not converge, the analysis will be replaced using LOCF as imputation method (see Section 4.2.1.11)

Prior TNF α inhibitor exposure and region are the stratification factors of the randomization. In the event that a study participant is stratified in the incorrect stratum (ie, the stratum recorded in the Interactive voice or web Response System (IXRS) differs from the actual stratum the study participant belongs to), the actual stratum will be used for the analysis.

The secondary analyses will be adjusted on the same categorical factors as the primary analysis. For continuous variables, Baseline value (of the variable of interest) will also be included as covariate where appropriate.

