2.4 Determination of sample size

Approximately 300 study participants will be randomly assigned in a 2:1 ratio to the following treatment groups: bimekizumab 160 mg sc (200 study participants) or placebo sc Q4W (100 study participants). The primary efficacy analysis is based on the bimekizumab dose versus placebo for ASAS40 response at Week 16. All sample size and power calculations were done at a significance level of 0.05 in a two-sided test.

All sample size and power calculations were performed using the software nQuery Advisor® 7.0.

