2.4.2 Power calculations for secondary endpoints in the hierarchical testing

The assumptions for power calculations of the secondary endpoints are based on the Week 12 results of AS0008, unless indicated otherwise. It was assumed that the treatment response at Week 12 and Week 16 would be the same (ie, conservative assumption). In addition, the observed data were adjusted in the same way as the primary endpoint to account for a higher number of study participants with prior TNF α inhibitor exposure and for a higher number of study participants with early withdrawal.

All power calculations for binary endpoints were performed using a 2-sided 2-sample Chi-square test with continuity correction (Fleiss et al, 1980). All power calculations for continuous endpoints were performed using a 2-sided 2-group Satterthwaite t-test (Moser et al, 1989). The power calculations provided below represent independent evaluations for each endpoint and do not account for multiplicity.

For ASAS40 response of the TNF α inhibitor-naïve population at Week 16, an ASAS40 response of 48% for the bimekizumab group was assumed. Placebo ASAS40 response at Week 16 is 18%. It is also assumed that 70% of the study participants in each treatment group are TNF α inhibitor-naïve. With those assumptions, the endpoint is powered with >99% at the planned sample size (ie, 140 and 70 study participants in the bimekizumab and placebo group, respectively).

For ASAS20 response at Week 16, an ASAS20 response of 70% for the bimekizumab group was assumed. Placebo ASAS20 response at Week 16 is 30%. With those assumptions, the endpoint is powered with 99% at the planned sample size.

For change from Baseline in BASDAI at Week 16, an adjusted between-treatment difference of -1.38 with an SD=1.8 for bimekizumab and SD=1.4 for placebo was used. With those assumptions, the endpoint is powered with >99% at the planned sample size.

For ASAS-PR at Week 16, an ASAS-PR of 17% for the bimekizumab group was assumed.

Placebo ASAS-PR at Week 16 was assumed to be 3.3%. With those assumptions, the endpoint is powered with 94% at the planned sample size.

For ASDAS-MI at Week 16, the ASDAS-MI data of AS0008 at Week 12 and Week 16 were used and the placebo response was extrapolated to Week 16. The assumed ASDAS-MI are 36.0% and 13.8% at Week 16 for the bimekizumab and placebo group, respectively. With those assumptions, the endpoint is powered with 98% at the planned sample size.

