4.2.1.11 Last Observation Carried Forward

The LOCF analysis will only apply for the continuous secondary efficacy endpoints that are part of the testing hierarchy, if the reference-based multiple imputation analysis does not converge (even after having dropped the covariates).

Post-Baseline missing data will be imputed by carrying forward the last available observation before the missing visit. Baseline data can be carried forward.

If a study participant has a value that is missing at Baseline, then the study participant will not be included in the analysis.

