8.1.4.3 Analysis on individual components of ASAS40

The change from Baseline in each individual component of the ASAS40 response (PGADA, total spinal pain score, BASFI, and BASDAI) will be analyzed at Week 16 using an analysis of covariance (ANCOVA) model. The analyses for the component variable BASFI will be described in Section 8.2.2 where analyses for secondary endpoints are described. For all four variables, the model will include treatment, prior TNF α inhibitor exposure and region as fixed effects and the respective Baseline values as covariate. These analyses will be done on the RS and will explore the effect of the signs and symptoms of the individual components on the composite endpoint.

The following 4 attributes describe the estimand that will be used to define the treatment effect of interest for each of the four components for this analysis:

- Population = Study participants enrolled according to the protocol-specified inclusion/exclusion criteria and randomized to IMP
- Study participant level outcome = The change from Baseline in the ASAS component variable at Week 16
- Intercurrent event handling = An intercurrent event is defined as discontinuation of study treatment due to any reason prior to Week 16. This estimand targets the treatment difference in a scenario where withdrawal from study treatment does not occur, such that outcomes for study participants without an IE are as observed, and outcomes for study participants with an IE are treated as they had completed the randomized study treatment through Week 16 but on placebo. In that strategy, missing data and non missing data after IE (reset as missing) will be imputed using reference-based MI, in which the MI model is based on data from the placebo group.
- Population-level summary measure = the difference in the adjusted means between bimekizumab and placebo.

Intermittent missing data will be imputed using the reference-based MI method as well. See Section 4.2.1.6 for technical details on how the reference-based MI method will be implemented.

The SAS[®] PROC MIXED will be used to run the ANCOVA model.

For each ANCOVA model specified in this analysis, the following statistics will be presented:

- a) For placebo and bimekizumab: the adjusted least-square means (LSM) and standard error (SE)
- b) For the comparison between placebo and bimekizumab: the difference between the LSM, the associated 95% confidence intervals for the contrasts, and the corresponding p-value.

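### For the continuous secondary endpoints in the testing hierarchy, the LOCF fallback targets a different, unstated estimand from the placebo-based one and may favour bimekizumab

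*SAP*

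**What the plan says.** Section 8.1.4.3 sets the estimand that Section 8.2.2 adopts for the continuous secondary endpoints in the hierarchy: outcomes after discontinuation "are treated as they had completed the randomized study treatment through Week 16 but on placebo". Section 4.2.1.6 implements it. Values after discontinuation are set to missing, missing post-Baseline values are imputed visit by visit from a model fitted to placebo data, missing Baseline values are imputed from all participants, and 100 analyses are combined by Rubin's rules.

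Section 4.1 allows the stratification factors to be dropped if a model fails to converge. For these endpoints, if the imputation still fails, "the analysis will be replaced using LOCF as imputation method". Table 4-1 (footnote g) marks LOCF as a primary method in that case. Section 4.2.1.11 defines it: "Post-Baseline missing data will be imputed by carrying forward the last available observation before the missing visit". Baseline may be carried forward, and if a Baseline value is missing "then the study participant will not be included in the analysis".

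Binary key secondary endpoints stay on non-responder imputation. Section 8.2.2 places BASMI outside the hierarchy, and I follow that here. However, its count of 11 key secondary endpoints matches the endpoints powered in Section 2.4.2 only if BASMI is included, so its status should be confirmed.

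**The concern.** A numerical failure would change the question being tested, inside the sequence that controls the family-wise error rate. Under the stated estimand, a bimekizumab participant who stops is given a placebo-like course. Under LOCF, the participant keeps the last available value, which is often one recorded on drug.

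Four further differences come with the switch:

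- **Uncertainty.** LOCF is a single imputation. Carried values are analysed as if observed, with no counterpart to Rubin's rules.
- **Population.** Section 8.2.2 analyses the Randomized Set, and reference-based imputation keeps participants with missing Baseline. LOCF drops them.
- **Values after discontinuation.** Section 4.2.1.6 sets them to missing and the observed-case rule in Section 4.2.1.10 excludes them. Section 4.2.1.11 is silent.
- **Trigger.** Section 4.1 describes non-convergence in terms of likelihood maximization, but the procedure is a series of imputation calls, visit by visit, repeated 100 times. The SAP does not say what counts as failure, or whether one failed call is enough.

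If the fallback were used, no placebo-based analysis would remain for that endpoint. The supportive methods in Table 4-1 are the hypothetical-estimand imputation and observed cases, and neither assumes placebo behaviour after discontinuation.

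**Working it through.** **Inputs from the SAP.** Section 2.4: "All sample size and power calculations were done at a significance level of 0.05 in a two-sided test"; "bimekizumab 160 mg sc (200 study participants) or placebo sc Q4W (100 study participants". Section 2.4.2: "All power calculations for continuous endpoints were performed using a 2-sided 2-group Satterthwaite t-test"; for BASDAI, "an adjusted between-treatment difference of -1.38 with an SD=1.8 for bimekizumab and SD=1.4 for placebo was used".

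**Step 1: reproduce the plan's figures.** The BASDAI standard error is √(1.8²/200 + 1.4²/100) = √(0.0162 + 0.0196) = 0.189, so the planned effect is 1.38/0.189 = 7.3 SE. Noncentral-t power with Satterthwaite degrees of freedom is above 99.99% for BASDAI and BASFI, 99.996% for nocturnal spinal pain, 99.08% for ASQoL and 99.99% for SF-36 PCS. The stated figure of >99% is confirmed for each.

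**Step 2: upper bound on the shift.** Let d be the share of bimekizumab participants who discontinue, and f the share of the Week 16 drug effect present in the carried value. The SAP gives neither, so both are assumptions.

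- Pure placebo outcome for discontinuers: (1 − d)Δ
- LOCF: (1 − d + d·f)Δ
- Gap: d·f·|Δ|

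For BASDAI, |Δ| = 1.38:

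| d | f = 0.5 | f = 1 | f = 1, in SE |
|---|---|---|---|
| 5% | 0.03 | 0.07 | 0.36 |
| 10% | 0.07 | 0.14 | 0.73 |
| 12% | 0.08 | 0.17 | 0.88 |
| 20% | 0.14 | 0.28 | 1.46 |

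At d = 10% and f = 1, the gap is 1.01 SE for BASFI, 0.60 for nocturnal spinal pain, 0.43 for ASQoL and 0.56 for SF-36 PCS.

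**Step 3: what the planned method does.** Section 4.2.1.6 predicts each visit from the participant's own earlier visits, so it retains part of any earlier benefit. If it retains a share r, the gap becomes d·f·(1 − r)·|Δ|. With r = 0.6 (assumed) and f = 1, this is 0.05 × 0.4 × 1.38 = 0.03 to 0.12 × 0.4 × 1.38 = 0.07.

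**Step 4: simulation for BASDAI.** 200,000 per arm; assumed Baseline 6.5, placebo change −1.0, SD 1.7, between-visit correlation 0.5 to 0.7, fast or slow onset.

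| Scenario | Placebo-based | LOCF |
|---|---|---|
| 10% random dropout, both arms | −1.27 to −1.29 | −1.30 to −1.34 |
| 20% dropout from Week 4 on, both arms | −1.19 to −1.25 | −1.32 to −1.38 |
| 15% bimekizumab, 5% placebo, slow onset, correlation 0.7 | −1.213 | −1.211 |

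The largest gap at equal dropout is about 0.135 (0.7 SE), toward bimekizumab; in the last scenario the methods coincide. With no drug effect and unequal dropout, LOCF moves by about 0.01 to 0.07 in either direction, while the placebo-based method stays near zero. A null shift of 0.07 is 0.37 SE, which would raise two-sided rejection from 5% to about 6.6%.

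**Step 5: effect on the decision.** At d = 12%, the pure-placebo figure is 0.88 × 1.38 = 1.21, or 6.4 SE. For ASQoL, the least well powered of the five, power under the pure-placebo bound is 98.4%, 97.3% and 93.2% at 5%, 10% and 20% discontinuation.

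**The case against.** The strongest reply is that the fallback is prespecified, remote and close to harmless. Imputing one visit at a time with few predictors should rarely fail once the covariates are dropped, and the planned effects are large. This stands, and it limits the weight of the point. It does not make LOCF answer the stated estimand.

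Several stronger readings are tempting and are not supported:

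- **That LOCF reverses the estimand.** It replaces it with another that is not stated. No simulated scenario with a drug effect changed sign.
- **That LOCF is chosen at table production, after unblinding.** In Section 4.1, the sentence about deciding at table creation governs the dropping of covariates. LOCF follows as a fixed last step, and Section 4.2.1.11 repeats that order. What is open is the definition of failure.
- **That discontinuers always receive an on-drug value.** Section 4.2.1.11 imputes only missing data, and Section 2.3 encourages participants who stop to keep attending. Read literally, an observed off-drug Week 16 value would be used as it is. Also, by Section 3.4, a last dose at Week 12 gives a discontinuation date of 84 + 28 + 3 = 115 days, after the nominal Week 16 visit at day 112, so some who stop are unaffected.
- **That LOCF always favours the drug.** Early stoppers may carry Baseline or a partial response, and placebo values are frozen too.

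The loss of participants with missing Baseline is probably small, since Section 3.3 substitutes Screening values. The effect on the standard error has not been quantified.

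**Conclusion.** The point holds for the continuous hierarchy endpoints only. The SAP names as primary fallback a method that does not estimate what Sections 8.1.4.3 and 8.2.2 define, and gives it no estimand of its own. It also changes the population, ignores imputation uncertainty and leaves the treatment of values after discontinuation unspecified.

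The shift in BASDAI is at most about 0.07 to 0.17 points (5% to 12% of the planned 1.38) if 5% to 12% of bimekizumab participants discontinue and all the benefit is carried forward. That bound treats the planned method as removing all benefit, which it does not, so the realistic shift is smaller and can be near zero. Discontinuation, retained benefit, correlation and time course are all assumptions. A changed conclusion is improbable. The change is still worth making, because it is cheap and concerns a primary rule within the multiplicity-controlled sequence.

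**What to change.** In Sections 4.1 and 4.2.1.11 and Table 4-1 (footnote g), replace LOCF as the primary fallback with a simplified reference-based imputation. It would be sequential and fitted to placebo data only, for example using Baseline and the preceding visit without the stratification factors. Keep the rest of Section 4.2.1.6: imputation of missing Baseline, values after discontinuation set to missing, and Rubin's rules.

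State what counts as non-convergence of the imputation, including whether a single failed call is enough, and fix the order in which terms are dropped. Delete LOCF, or keep it as supportive only and then say how values after discontinuation are handled.

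The cost is SAP wording and a small code branch. No additional data are needed.

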4.2 Handling of dropouts or missing data

4.2.1 Handling of Missing data for efficacy analyses

Different approaches will be used to handle missing data and intercurrent events for all endpoints as summarized in Table 4-1 below. Details of the estimand structures and statistical analyses are described in Section 8 and details of the imputation methods are described in the following sections.

Table 4-1: Missing data handling methods for efficacy endpoints

Variable Priority	Variable Type	Composite Estimand (NRI)	Modified Composite Estimand (MI)	Tipping Point	Treatment Policy	Reference-based (MI)	Hypothetical Estimand (MI)	OC	LOCF
Primary	Binary	P	S ^a	S ^a	S ^a			S	
Secondary included in statistical testing procedure	Binary	P	S ^a					S	
	Continuous					P	S	S	P ^g
Secondary not included in statistical testing procedure	Binary	X	X					X	
	Continuous						X	X	
Other	Binary	X	X					X	
	Continuous					X ^e	X ^d	X ^b	
	Categorical						X ^f	X ^c	

P=Primary method, S=Supportive method, X=Method to be used (no priority designated).

Note: Composite estimand (NRI) refers to the approach in which data preceded by the intercurrent event of study treatment discontinuation for any reason are imputed as non-response, and other missing data are also imputed as non-response.

Note: Modified Composite Estimand (MI) refers to the approach in which data preceded by the intercurrent event of study treatment discontinuation due to AE (including death) or lack of efficacy are imputed as non-response, and other missing data are imputed via a multiple imputation model.

Note: Tipping Point refers to the approach in which missing data and data preceded by the intercurrent event of study treatment discontinuation for any reason are multiply imputed and then adjusted.

Note: Treatment Policy refers to the approach in which intercurrent events are not considered and all missing data are multiply imputed, and all other data are as observed.

Note: Hypothetical Estimand (MI) refers to the approach where outcomes for study participants without an intercurrent event of study treatment discontinuation are as observed, and outcomes for study participants with missing data or with an intercurrent event for any reason are imputed via a multiple imputation model.

^a Imputation method is applied on continuous data, and binary variable is derived from the continuous variable based on imputed data set.

^b Required only for by-visit summaries of variables whose value at Week 16 is part of the hierarchical testing procedure.

^c For variables with multiple categories, data will be summarized as observed with an additional missing row to capture missing data at a given visit.

^d MI will not be performed for the change from baseline in WPAI-SHP, change from baseline in EQ-5D-3L Utility Scores, change from Baseline in ASspiMRI-a (Berlin modification) score, or change from baseline in SPARCC score where only observed case analysis will be performed.

^e Performed only for components of the primary endpoint.

^f MI analysis will only be required for ASDAS status endpoint.

^g Last Observation Carried Forward (LOCF) will only be used for the secondary continuous endpoints in the hierarchy if the Reference-Based Multiple Imputation analyses do not converge.

In this section, two terms will be defined for binary endpoints:

- Binary endpoints derived based on one continuous measurement (eg, BASDAI50 at Week 16) will be called ‘non-composite binary endpoint’.
- Binary endpoints derived based on several continuous measurements (eg, ASAS40 at Week 16), will be called ‘composite binary endpoint’.

4.2.1.1 Handling of Missing data for the Primary Endpoint

Because the ASAS40 composite binary primary endpoint is based on 4 different component scores, it is necessary to consider various data scenarios that could impact the calculation of the response. The rules described here are applicable in the context of the calculation of ASAS40 response and may differ from the rules applied for calculating and summarizing the components individually (some values may need to be imputed for component analysis but are not required here to evaluate the ASAS response). It is expected that cases using the following rules will occur infrequently, especially cases of 0 results at Baseline, as study participants are required to have moderate to severe active AS at study entry. The following rules will be applied prior to invoking any imputation analysis at the variable level (including observed case analysis), unless when specified differently:

- If a study participant has any component value that is equal to 0 at Baseline, then the following will be done:
 - If the post-Baseline value is equal to 0, then the absolute and percent improvement for that component will be treated as 0 for purposes of ASAS response calculations.
 - If the post-Baseline value is greater than 0, then the component is treated as having a 20% worsening and a 1-unit absolute worsening from Baseline for purposes of ASAS response calculation.
- If a study participant has any component value that is missing at Baseline, then the absolute and percent improvement for that component will be treated as 0 across all visits for purposes of ASAS response calculation.
- If at least 3 of the 4 components have observed data collected, the ASAS response will be calculated based on observed data. If 3 observed components show improvement, it is assumed that the 4th domain will not worsen.

For the primary analysis based on NRI (see Section 8.1.2 for details), if there are fewer than 3 components with observed data at a given post-Baseline visit, then the study participant will be classified as "non-responder", consistent with the pre-defined approach for handling intercurrent events defined in Section 8.1. For addressing missing components in supportive analyses, the following rules will be implemented for the primary endpoint ASAS40 only:

- Modified Composite Estimand - Multiple Imputation

Multiple imputation will be applied on missing data, and data that are collected after the date of intercurrent event (IE) as defined in Section 3.4. If there are fewer than 3 components with observed data (considering all observed data after the IE date as missing), each of the components will be imputed separately before deriving the response; the available observed values and the imputed values will be used to derive the response. Study participants with IEs, will then be considered non-responders at all time points after the IE date. Analysis details are presented in Section 4.2.1.4.2 and Section 8.1.4.4.

- The tipping point approach:

The tipping point approach implemented if the primary endpoint analysis result is statistically significant at alpha=0.05. The tipping point approach will first include a Worst Case imputation:

- All data after the date of IE for treatment discontinuation due to any reason will be set to missing.
 - If at least 3 of the 4 components have observed data collected and where possible, the ASAS response/non-response will be calculated based on observed data.
 - If fewer than 3 components have observed data, then study participants treated with bimekizumab will be classed as non-responders, while study participants treated with placebo will be classed as responders.

If the significant result remains, then no further analysis is necessary.

- If the result changes as a result of the worst-case approach, then imputation with delta adjustments will be made to each missing component before deriving the ASAS endpoint to establish the 'tipping point' at which the result changes.

A similar approach to that described above for the Modified Composite Estimand - Multiple Imputation will be implemented for the Delta Adjustment approach. However, study participants with treatment discontinuation will not be automatically considered non-responders at all timepoints after the IE date. Instead, missing data and data after the IE date for treatment discontinuation for any reason will be imputed and adjusted, and the imputed and adjusted data will be used, together with observed data, to derive the response. These approaches are described in detail in Section 4.2.1.8 and Section 8.1.4.7.

- The treatment policy strategy:

A similar approach to that described above for the Modified Composite Estimand - Multiple Imputation will be implemented with the difference being that study participants with treatment discontinuation will not be set to missing prior to imputation and will not be automatically considered non-responders at all time points after the IE date. Specifically:

- If at least 3 of the 4 components have observed data collected and where possible, the ASAS response/non-response will be calculated based on observed data.
- If there are fewer than 3 components with observed (on and off treatment) data at a given post-Baseline visit, then multiple imputation methods will be applied, where any observed data after treatment discontinuation will be as observed (ie, NOT set to missing) and will not automatically be switched to non-response. Missing data for each of the components will be imputed separately before deriving the response based on imputed components. Details of this approach are presented in Section 4.2.1.9 and Section 8.1.4.5.
- The OC analysis:
 - If at least 3 of the 4 components have observed data collected and where possible, the ASAS response/non-response will be calculated based on observed data for study participants that are still on the original randomized treatment; data collected after the treatment discontinuation for any reason will not be included.
 - If there is partial missing data for ASAS and from the observed data is it clear that the study participant could not possibly be a responder, then the study participant will be coded as a non-responder and will be counted in the denominator of the OC analysis. For example, this could happen if:
 - there are 2 observed components and at least one shows worsening, or
 - there are 2 observed components and both show no response, or
 - there is only one observed component and it shows worsening.
 - In the other cases, the response will be missing and the study participant will not be included in the OC analysis. Details of this analysis are described in Section 4.2.1.10 and Section 8.1.4.6.

